## 1 INTRODUCTION

### 1.1 STUDY DESIGN

This study is a multi-center, 24-week treatment, parallel group, double-blind, randomized, placebo-controlled study to evaluate the use of dupilumab in participants with prurigo nodularis (PN) inadequately controlled on topical prescription therapies or when those therapies are not advisable. The study will assess the effect of dupilumab on itch improvement as well as its effect on PN lesions, on participants' health-related quality of life (HRQoL), anxiety and depression, sleep quality, skin pain, and overall health status.

After 2-4 weeks of screening, participants will be centrally randomized using a permuted block randomization schedule via Interactive Voice Response System/Interactive Web Response System (IVRS/IWRS) in a 1:1 randomization ratio to dupilumab 300 mg q2w or matching placebo.

Randomization will be stratified by documented history of atopy (atopic or non-atopic), stable use of topical corticosteroids (TCS)/ topical calcineurin inhibitors (TCI) (yes or no), and country/territory code.

A total of approximately 150 participants will be randomized to two treatment arms (75 participants/arm). The number of participants with active mild AD upon study entry will represent up to 10% of the atopic participants. Both the atopic and the non-atopic PN populations will each be capped at 60% of the total enrolled population.

The study duration consists of the following periods:

- Screening period (2-4 weeks)
- Randomized IMP intervention period (24 weeks)
- Follow-up period (12 weeks)

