## 2 SAMPLE SIZE DETERMINATION

The primary endpoint is the proportion of participants with WI-NRS reduction of  $\geq 4$  from baseline to Week 12. By assuming the response rate is [REDACTED] in the placebo and dupilumab arms, respectively, 56 participants/arm will provide 90% power to detect the difference of [REDACTED] between dupilumab and placebo with Fisher exact test at 2-sided level of 0.05. Assuming 15% drop out during the 12 weeks of treatment, the target is to randomize 75 participants/arm with a cap of up to 10% of participants in the atopic population having active mild AD.

The assumptions were based on the effect of dupilumab versus placebo in WI-NRS reduction  $\geq 4$  at Week 16 observed in participants with moderate to severe AD as seen in studies of AD-1334 (Solo1) and AD-1416 (Solo2).

Approximately 150 participants will be randomized to dupilumab or placebo in a 1:1 ratio with stratification factors of documented history of atopy (atopic or non-atopic), stable use of TCS/TCI (yes or no), and country/territory code. Both the atopic and the non-atopic PN population will be capped at 60% of the total enrolled population.

The sample size calculation was performed using SAS 9.4 power procedure.

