Each of the imputed complete data will be analyzed by fitting an ANCOVA model as described above. The imputation number will be about 40. Statistical inference obtained from all imputed data will be combined using Rubin's rule. Descriptive statistics including number of participants, mean, standard error, and least squares (LS) mean changes (and standard error) will be provided. In addition, difference of the dupilumab group against placebo in LS means and the corresponding 95% confidence intervals (CI) will be provided along with the p-values.

See [Section 5.5](#) for the sample SAS code for the imputation and the analysis.

For the endpoint of percent change from baseline in WI-NRS at week 24, we will also perform an as-observed plus multiple imputation supplementary analysis as described below.

The data collected after taking all prohibited medications and/or rescue medications will be included in the supplementary analysis to evaluate the robustness of the primary analysis results with respect to the method of handling data while taking the prohibited medications (e.g. treatment policy strategy). In addition, for participants discontinuing the study treatment before Week 24, their off-study treatment values measured up to Week 24 will be included in the analysis. For participants having missing data at Week 24 regardless of reason(s), a multiple imputation (MI) approach will be used to impute the missing endpoint value.

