#### **4.6 MULTIPLICITY ISSUES**

The multiplicity procedure is proposed to control the overall type-I error rate for testing the primary and selected secondary endpoints. The overall alpha is 0.05. The comparisons with placebo will be tested based on the hierarchical order below at 2-sided  $\alpha = 0.05$ :

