### **5.3 APPENDIX 3 DEMOGRAPHICS AND BASELINE CHARACTERISTICS, PRIOR OR CONCOMITANT MEDICATIONS/PROCEDURES**

#### ***Demographics, baseline characteristics, medical surgical history***

The following demographics and baseline characteristics, medical and surgical history and disease characteristics at baseline will be summarized using descriptive statistics in the randomized population.

Demographic variables are

- Age in years (quantitative and qualitative variable: 18-<40, 40-<65, 65-<75, and  $\geq 75$  years),
- Gender (Male, Female),
- Race (White, Black or African American, Asian, American Indian or Alaska Native, Native Hawaiian or other Pacific Island, unknown),
- Ethnicity (Hispanic or Latino, Not Hispanic or Latino, Unknown)
- Region (Asia: Taiwan, South Korea; East Europe: Hungary; Latin America: Chile; Western Countries: USA, Canada, France, Italy, Portugal, Spain, and UK)
- Territory (North America: USA, Canada; European Union: France, Italy, Portugal, Spain, Hungary, and UK; Rest of World: Taiwan, South Korea, Chile)
- Weight in kg (quantitative and qualitative variable: (<60,  $\geq 60$ - <90,  $\geq 90$  kg)
- BMI in kg/m^2 (quantitative and qualitative variable: <25,  $\geq 25$ - <30,  $\geq 30$  kg/m^2)

Baseline safety and efficacy parameters (apart from those listed above) will be presented along with the safety and efficacy summaries.

Medical (or surgical) history includes all the relevant medical (or surgical) history during the lifetime of the participant.

This information will be coded using the version of MedDRA currently in effect at Sanofi at the time of database lock.

Comorbidity will be summarized separately. The following comorbid diseases will be summarized from electronic case report form (eCRF) pages which were filled in by investigators based on participant reporting.

- Prurigo nodularis (Yes, Ongoing condition)
- Atopic dermatitis (Yes, Ongoing condition)
- Allergic rhinitis history (Yes, Ongoing condition)
- Allergic rhinoconjunctivitis (Yes, Ongoing condition)
- Asthma history (Yes, Ongoing condition)

- Food allergy history (Yes, Ongoing condition)
- Eosinophilic esophagitis history (Yes, Ongoing condition)

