## 5.5 APPENDIX 5 SAMPLE SAS CODE

The multiple imputation and analysis model for the primary analysis of change from baseline in WI-NRS at Week 12 will be built with the following sample SAS code.

1. 40 datasets with a monotone missing pattern will be obtained, induced by Markov Chain Monte Carlo (MCMC) method on participants who have not taken the prohibited medications and/or rescue medications or have discontinued study treatment due to lack of efficacy prior to Week 12.

```
proc mi data=dat_etd seed=16460 n impute=40 out=dat_mc;  
  mcmc impute=monotone;  
  var atopicyн stableyn region antidblyn trt01p winrsbl chg1winrs ...  
    chg24winrs;  
  run;
```

2. For each of the imputed dataset with monotone missing pattern in step 1, the remaining missing data will be imputed using the regression method for the monotone pattern with adjustment for covariates including intervention groups, documented history of atopy (atopic or non-atopic), stable use of TCS/TCI (yes or no), region, baseline anti-depressant use (yes or no), and baseline value of the response variable.

```
proc mi data=dat_mc n impute=1 seed=16461 out=dat_mi;  
  by _imputation_;  
  class atopicyн stableyn region antidblyn trt01p;  
  monotone method=reg;  
  var atopicyн stableyn region antidblyn trt01p winrsbl chg1winrs ...  
    chg24winrs;  
  run;
```

3. Each of the 40 imputed datasets will be merged with the one dataset imputed by WOCF approach, and then be analyzed using the main statistical model. These 40 imputed datasets will be saved.

```
%macro w1;  
  %do i=1%to 40;  
    data wocf&i.;  
    set wocf;  
    _imputation_=&i.;  
    run;  
  %end;  
  data wocf_all;  
  set %do j=1 %to 40; wocf&j. %end;;  
  run;  
%mend w1;
```

```
%w1

data dat_imp;
  set dat_mi  wocf_all;
Run;

proc sort data=dat_imp;
  by _imputation_;
run;

proc glm data= dat_imp;
  by _imputation_;
  class atopicyn stableyn region antidblyn trt01p;
  model chg24winrs = atopicyn stableyn region antidblyn
    trt01p winrsbl;
  lsmeans trt01p / stderr;
  estimate 'Diff Dupilumab vs Placebo' trt01p -1 1;
  ods output LSMeans=implsmeans Estimates=implsmeandiff;
run;
```

4. Applying Rubin's rule to combine analysis results (point estimates and standard errors) from 40 imputations using PROC MIANALYZE for the LS means and difference in LS means between dupilumab and placebo. Sample code:

```
proc sort data=implsMeans; by trt01pn _imputation_; run;

proc mianalyze data= implsmeans;
  by trt01pn;

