  modeleffects lsmean;
  stderr stderr;
  ods output ParameterEstimates=lsmeans;
run;

proc mianalyze data=implsmeandiff;
  modeleffects estimate;
  stderr stderr;
  ods output ParameterEstimates=lsmeandiff;
run;
```

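### The sample pooling code gives PROC MIANALYZE no complete-data degrees of freedom, so run as written it makes the intervals for five hierarchy endpoints about 1% too narrow and adds about 0.2 points to their nominal level

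*SAP*

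**What the plan says.** SAP 4.4.2 (continuous secondary efficacy endpoints) fits an ANCOVA to each of about 40 imputed datasets and continues: "Statistical inference obtained from all imputed data will be combined using Rubin's rule". It refers to Appendix 5 (section 5.5) for sample code.

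In that code, step 3 fits the ANCOVA in PROC GLM ("model chg24winrs = atopicyn stableyn region antidblyn", then treatment and baseline). Step 4 makes two pooling calls, one for the LS means and one for the treatment difference, the latter opening "proc mianalyze data=implsmeandiff". Each passes an estimate and a standard error and nothing else. Neither carries EDF=, and I found no statement elsewhere in the SAP of the degrees of freedom for the pooled tests.

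SAP 4.6 sets the error rate: "The overall alpha is 0.05", and "The comparisons with placebo will be tested based on the hierarchical order below at 2-sided" 0.05. Both regional hierarchies contain the same five continuous endpoints at Week 24: percent change in WI-NRS, DLQI, skin Pain-NRS, Sleep-NRS and HADS total score. The first two use this method through 4.4.2. The other three are exploratory endpoints and reach it through 4.5.2, which applies the secondary-endpoint methodology to similar data.

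**The concern.** If PROC MIANALYZE is not told the complete-data degrees of freedom, it treats them as infinite and uses the classical Rubin formula. (This is a property of the software; the documents do not state it.) With 40 imputations and modest missingness the result runs into the thousands, although a single completed dataset supports only about 141.

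The limiting case shows the inconsistency. With nothing missing, the SAP's own PROC GLM step would refer the treatment contrast to t on 141 degrees of freedom, critical value 1.977. Passing the same estimate and standard error through the pooling step would refer it to essentially 1.960. Imputation should not sharpen the reference distribution.

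At stake is the width of the reported intervals for five endpoints and, in a fixed-sequence test, whether a borderline p-value lets testing continue.

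**Working it through.** **Inputs from the SAP**
- Sample size (1.1): "A total of approximately 150 participants will be randomized to two treatment arms (75 participants/arm").
- Imputations (4.4.2 and Appendix 5): m = 40.
- Region (Appendix 3): "Region (Asia: Taiwan, South Korea; East Europe: Hungary; Latin America: Chile; Western Countries: USA, Canada, France, Italy, Portugal, Spain, and UK"), so four levels and 3 df.
- ANCOVA parameters (Appendix 5, step 3): intercept 1 + atopy 1 + TCS/TCI 1 + region 3 + antidepressant 1 + treatment 1 + baseline 1 = 9.
- Complete-data df: ν_com = 150 − 9 = 141.

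**Assumption.** The fraction of missing information γ is not in the documents. The only attrition figure is "Assuming 15% drop out during the 12 weeks of treatment", which covers 12 weeks rather than 24 and is not itself a γ. I take γ = 5, 10 and 15%.

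**Formulas**, where r is the between- to within-imputation variance ratio (including the factor 1 + 1/m) and γ = r/(1 + r):
- No EDF=: ν = (m − 1)(1 + 1/r)² = 39/γ².
- Barnard-Rubin: ν_obs = [(ν_com + 1)/(ν_com + 3)] · ν_com · (1 − γ), then 1/ν_BR = 1/ν + 1/ν_obs.
- Nominal level of the code as written: 2·P(t with ν_BR df > critical value at ν).

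**One line in full, γ = 10%.** ν = 39/0.01 = 3900. ν_obs = (142/144) × 141 × 0.90 = 125.1. ν_BR = 1/(1/3900 + 1/125.1) = 121.2.

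| γ | df, no EDF= | df, Barnard-Rubin | critical value, no EDF= | critical value, Barnard-Rubin | interval width ratio | nominal level |
|---|---|---|---|---|---|---|
| 5% | 15,600 | 131.0 | 1.9601 | 1.9782 | 0.991 | 5.21% |
| 10% | 3,900 | 121.2 | 1.9606 | 1.9797 | 0.990 | 5.22% |
| 15% | 1,733 | 110.6 | 1.9613 | 1.9816 | 0.990 | 5.24% |

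With no missing data the limit is 1.9600 against 1.9769, a width ratio of 0.991 and a level of 5.20%. With r as large as 1 (γ = 50%) the nominal level is 5.40%.

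**Which p-values could change.** A test that sits exactly at 0.05 under Barnard-Rubin would be reported by the code as written as 0.0479, 0.0478 or 0.0477 at the three values of γ. Only reported p-values from about 0.048 to 0.050 are in play.

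**Simulation.** Null trials with N = 150, the same nine-parameter ANCOVA and m = 40; 40,000 trials per scenario, Monte Carlo standard error 0.11 points. The missing-data shares are assumed.

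| Scenario | Size, no EDF= | Size, EDF=141 |
|---|---|---|
| Nothing missing | 5.14% | 4.91% |
| 8% multiply imputed | 5.24% | 5.03% |
| 15% multiply imputed | 4.99% | 4.82% |
| 8% multiply imputed, 12% WOCF | 4.90% | 4.67% |
| 8% multiply imputed, 25% WOCF | 5.23% | 4.98% |

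Leaving out EDF= raises the rejection rate in every scenario, by 0.17 to 0.25 points. The absolute size moves around for other reasons.

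**The case against.** - **It is sample code.** The appendix says so, its variable lists contain ellipses, and it is introduced for change in WI-NRS at Week 12 while modelling the Week 24 variable. An option missing from a template is not a decision to use infinite df, and the final programs may differ. This stands, and it limits the point to the code if run as written. But the SAP contains no other detail on pooling, so nothing in it would lead a programmer to the small-sample rule.
- **Classical Rubin degrees of freedom are Rubin's rule.** True: the code does not contradict 4.4.2, and Barnard-Rubin is a refinement. The text simply does not say which is meant.
- **A reader might infer that these tests truly run at 5.2%.** The documents do not support that. The 5.2% is the degrees-of-freedom effect alone. The method in 4.4.2 is a hybrid of WOCF and multiple imputation, and its actual size depends on the WOCF component and on missingness that the documents do not give. In the simulations the code as written ran from 4.9% to 5.2%.
- **A reader might also infer that trial success is exposed.** It is not. The main analyses of the primary and key secondary endpoints are CMH tests with non-responder imputation and do not use this step. SAP 4.6 ties a positive study to the primary endpoint alone. The first continuous endpoint is sixth in the US order and fourth elsewhere.
- **The effect is negligible in practice.** It is small, and other approximations in the analysis may be of similar size. That makes this a minor item, but the correction is equally small.

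**Conclusion.** The point holds as a minor coding correction. Relative to the small-sample rule, the sample code as written makes the pooled intervals about 1% too narrow and adds about 0.2 percentage points to the nominal two-sided level for the five continuous endpoints in the hierarchy.

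This rests on three assumptions: the software default when EDF= is absent; 5 to 15% missing information; and 141 error degrees of freedom, which requires 150 participants and all four regions in the model. The conclusion is not sensitive to the last: with 100 participants and the same nine parameters (91 df), the no-missing-data level is 5.31% instead of 5.20%.

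**What to change.** Add EDF= to both PROC MIANALYZE calls in Appendix 5 step 4. Set it to the error degrees of freedom that PROC GLM actually reports for the endpoint, rather than hard-coding 141. State in SAP 4.4.2 that Rubin's rule is applied with the Barnard-Rubin small-sample degrees of freedom, so that the rule also covers skin Pain-NRS, Sleep-NRS and HADS through 4.5.2.

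The cost is one option per call and one sentence. Estimands, point estimates and standard errors do not change. The downside is that p-values and intervals become very slightly less favourable, and in some missing-data patterns the test may be marginally conservative: the lowest simulated size with EDF=141 was 4.67%, about three Monte Carlo standard errors below 5%.

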## 5.6 APPENDIX 6 SELECTION CRITERIA FOR AE/MEDICATION GROUPINGS

Table 14 - List of PTs or Medications for CMQs/CDGs

Grouping	Preferred Term/Medication Code	Preferred Term/Medication
Conjunctivitis	10001257	Adenoviral conjunctivitis
Conjunctivitis	10010725	Conjunctival irritation
Conjunctivitis	10010726	Conjunctival oedema
Conjunctivitis	10010736	Conjunctival ulcer
Conjunctivitis	10010741	Conjunctivitis
Conjunctivitis	10010744	Conjunctivitis allergic
Conjunctivitis	10010745	Conjunctivitis chlamydial
Conjunctivitis	10010749	Conjunctivitis gonococcal neonatal
Conjunctivitis	10010754	Conjunctivitis tuberculous
Conjunctivitis	10010755	Conjunctivitis viral
Conjunctivitis	10018258	Giant papillary conjunctivitis
Conjunctivitis	10021629	Inclusion conjunctivitis
Conjunctivitis	10030861	Ophthalmia neonatorum
Conjunctivitis	10048908	Seasonal allergy
Conjunctivitis	10049458	Herpes simplex virus conjunctivitis neonatal
Conjunctivitis	10051625	Conjunctival hyperaemia
Conjunctivitis	10053991	Inclusion conjunctivitis neonatal
Conjunctivitis	10061784	Conjunctivitis bacterial
Conjunctivitis	10062889	Pingueculitis
Conjunctivitis	10063669	Photoelectric conjunctivitis
Conjunctivitis	10067317	Oculorespiratory syndrome
Conjunctivitis	10067817	Acute haemorrhagic conjunctivitis
Conjunctivitis	10069166	Blebitis
Conjunctivitis	10071570	Ligneous conjunctivitis
Conjunctivitis	10074701	Noninfective conjunctivitis
Conjunctivitis	10075264	Oculoglandular syndrome
Conjunctivitis	10080825	Conjunctivitis fungal
Conjunctivitis	10084034	Conjunctival suffusion
Intravenous immunoglobulin therapy	CAS 8000012671	IMMUNOGLOBULIN HUMAN NORMAL
Intravenous immunoglobulin therapy	CAS 8000050682	IMMUNOGLOBULIN, PORCINE
Intravenous immunoglobulin therapy	CAS 8000056919	IMMUNOGLOBULIN G HUMAN

Grouping	Preferred Term/Medication Code	Preferred Term/Medication
Intravenous immunoglobulin therapy	CAS 8600000563	IMMUNOGLOBULINS NOS
Intravenous immunoglobulin therapy	CAS 8600001670	IMMUNOGLOBULIN HUMAN NORMAL SLRA
Intravenous immunoglobulin therapy	CAS 8600001671	IMMUNOGLOBULIN HUMAN NORMAL IFAS
Intravenous immunoglobulin therapy	RECNO 900708	OTHER IMMUNOGLOBULINS
Intravenous immunoglobulin therapy	RECNO 900722	IMMUNE SERA AND IMMUNOGLOBULINS
Intravenous immunoglobulin therapy	RECNO 900728	IMMUNOGLOBULINS
Intravenous immunoglobulin therapy	RECNO 900914	SPECIFIC IMMUNOGLOBULINS
Intravenous immunoglobulin therapy	RECNO 901112	IMMUNOGLOBULINS, NORMAL HUMAN

Abbreviations: CAS : Chemical Abstract Service Registry Number RECNO : Drug Record Number

## 5.7 APPENDIX 7 MEDICATION/PROCEDURE ADJUDICATION ALGORITHM

### Algorithm for determining whether treatment with following medications or procedures constitutes treatment failure resulting in setting data as non-responder after taking medication or undergoing procedure in the main statistical analysis

1. Not required to adjudicate post-baseline medications (WHODD-coded) or procedures (CMQ-coded) as these will be considered treatment failures if used at any time.
  - a) Always considered treatment failure
    - ATC2 = CORTICOSTEROIDS FOR SYSTEMIC USE
    - ATC2 = IMMUNOSUPPRESSANTS (systemic, e.g. oral or parenteral route)
    - Preferred Drug Name = Ciclosporin
    - Preferred Drug Name = Methotrexate
    - Preferred Drug Name = Mycophenolate sodium
    - Preferred Drug Name = Mycophenolic acid
    - Preferred Drug Name = Azathioprine
    - Preferred Drug Name = Gabapentin
    - Preferred Drug Name = Pregabalin
    - Preferred Drug Name = Thalidomide
    - Preferred Drug Name = Lenalidomide
    - Preferred Drug Name = Baricitinib
    - Preferred Drug Name = Ruxolitinib
    - Preferred Drug Name = Tofacitinib
    - Preferred Drug Name = AbrocitinibPreferred Drug Name = Delgocitinib
    - Preferred Drug Name = Nalbuphine
    - Preferred Drug Name = Naltrexone
    - Preferred Drug Name = Naloxone
    - Preferred Drug Name = Vixarelimab
    - Preferred Drug Name = Nemolizumab
    - Preferred Drug Name = Serlopitant
    - Preferred Drug Name = Aprepitant
    - CMQb HLT Phototherapies
    - CMQ Tanning\_single PT

b) Never considered treatment failure:

- ATC2 = EMOLLIENTS AND PROTECTIVES
- ATC2 = GENERAL NUTRIENTS
- ATC2 = VITAMINS
- ATC2 = ANTIVIRALS FOR SYSTEMIC USE
- ATC2 = ANTIFUNGALS FOR DERMATOLOGICAL USE
- ATC2 = ANTISEPTICS AND DISINFECTANTS
- ATC2 = ANTIBIOTICS AND CHEMOTHERAPEUTICS FOR DERMATOLOGICAL USE
- ATC2 = ANTI-ACNE PREPARATIONS, excluding D10AA Corticosteroids, combinations for treatment of acne
- ATC2 = OPHTHALMOLOGICALS
- ATC1 = ANTIINFECTIVES FOR SYSTEMIC USE, excluding D07C Corticosteroids, combinations with antibiotics
- ATC1 = BLOOD AND BLOOD FORMING ORGANS
- ATC1 = ALIMENTARY TRACT AND METABOLISM
- ATC1 = MUSCULO-SKELETAL SYSTEM, excluding M01BA Antiinflammatory/antirheumatic agents in combination with corticosteroids
- ATC2 = COUGH AND COLD PREPARATIONS
- ATC2 = PSYCHOLEPTICS, excluding N05BB Diphenylmethane derivatives and N05C HYPNOTICS AND SEDATIVES

 A blinded review of all post-baseline medications or procedures to adjudicate whether treatment constitutes treatment failure, based on medical judgment, may be performed in addition. A listing of treatments or procedures classified as treatment failure in a manner inconsistent with the classification under #1 will be provided, along with supporting rationale.

**2. Require to adjudicate medications or procedures that may constitute treatment failure**

- All other medications and procedures listed in the protocol and **Table 5** of the SAP (not noted in 1. above) given for indications consistent with PN
- Considerations in determining treatment failure include the criteria already set forth in **Table 5** of the SAP in addition to the type of medication or procedure, indication, dose, route of administration, timing, frequency and the potential impact of the use of the prohibited medications/procedures and rescue medications on the primary and key secondary efficacy endpoints.

2 Below is a list of indications consistent with PN based on PT level from concomitant medication/procedure data using MedDRA dictionary

System Organ Class	High Level Term	Preferred Term	Preferred Term Code
Skin and subcutaneous tissue disorders	Dermatitis and eczema	Neurodermatitis	10029263
Infections and infestations	Bacterial infections NEC	Eczema impetiginous	10051890
Infections and infestations	Skin structures and soft tissue infections	Dermatitis infected	10012470
Infections and infestations	Skin structures and soft tissue infections	Eczema infected	10014199
Skin and subcutaneous tissue disorders	Dermatitis and eczema	Dermatitis	10012431
Skin and subcutaneous tissue disorders	Dermatitis and eczema	Dermatitis atopic	10012438
Skin and subcutaneous tissue disorders	Dermatitis and eczema	Eczema	10014184

